**COMPLIANCE STATEMENT**

This study will be conducted in compliance with the Declaration of Helsinki as well as all applicable local regulations.

## SYNOPSIS

Title:	A Prospective, Multicenter, Randomized Controlled Study to Evaluate the Wound Closure Efficiency of [REDACTED] Knotless Tissue Control Device [REDACTED] Compared to Conventional Sutures in Total Knee Arthroplasty (TKA)
Protocol Number:	ESC-16-001
Regulatory Status:	Post-Marketing All wound closure products used in the study are legally market in China and should be used within their approved indications.
Indication:	[REDACTED] Device is indicated for use in soft tissue approximation where the use of absorbable sutures is appropriate.
Objectives:	The primary objective of this prospective, randomized controlled study is to evaluate the wound closure efficiency of [REDACTED] compared to conventional sutures in patients undergoing TKA. For the purpose of this study, wound closure efficiency is defined as the total time required to close the surgical incisions in patients undergoing TKA procedures using [REDACTED] compared to those using traditional sutures. Secondary objectives will include the evaluation of differences in overall surgical procedure time, operating room (OR) time, length of stay, procedure costs, quality of life measures including pain, and range of motion (ROM). In addition, the difference in the safety profiles for both wound closure procedures will be evaluated through the analysis of the incidence of wound complications including dehiscence, wound infections, and other adverse events.

Endpoint:	
Primary Efficacy Endpoints:  The primary endpoint will be the total time required to close the surgical incisions between treatment groups. The time to close each surgical incision is defined as the time in minutes between placement of the first suture throw in the deep tissue and the completion of intradermal layer closure (capturing the suturing time only).
 
Secondary Efficacy Endpoints:
 
 
1. Duration of procedure;
 
2. Overall OR time;
 
3. Length of stay between surgery and discharge; and
 
4. TKA related QoL assessments: 
 
a. Knee pain;
 
b. Health-related quality of life (EQ-5D-3L);
 
 
 
 
Secondary Safety Endpoints:
 
 
1. The incidence of surgical site infection (SSI) following surgery as defined by CDC criteria;
 
2. ASEPSIS score (only for subjects with confirmed SSI);
 
3. Acute Inflammatory Response Evaluation (AIRE) score;
 
4. Incidence of wound separation or dehiscence requiring intervention;
 
5. Incidence of delayed wound healing events; and
 
6. Incidence of adverse events (AEs) and serious adverse events (SAEs) associated with wound closure;
 

Study Design:	
This is a multicenter, single blind, prospective, randomized controlled study in patients undergoing elective TKA and meeting the study's eligibility criteria. Eligible patients will be randomized on 1:1 basis to have the surgical incision closed with either [REDACTED] or conventional sutures. Wound closure and surgical procedure times will be determined perioperatively. Patients will remain blinded to the type of sutures utilized for closure of the incision.

Number of Subjects (Planned):	184 subjects (92 per arm)
Duration of Study	
Enrollment is anticipated to require approximately 8 months. The duration of the study is therefore expected to be approximately 9 months from the date of the first patient enrolled to the last patient taking into account the 4-6 weeks follow-up period.

Diagnosis/Criteria for Inclusion:	
 
1. Patient is <math>\geq</math> 18 years and <math><</math> 80 years of age;
 
2. Patient with osteoarthritis is scheduled to undergo elective unilateral TKA;
 
3. Patient is willing to participate in the study, comply with study requirements, follow-up schedule, and give written informed consent; and
 
4. Patient agrees not to schedule any additional elective surgical procedures until participation in this study is complete.
 

Diagnosis/Criteria for Exclusion:	
 
1. Female patient who is pregnant or lactating at the time of screening;
 
2. Patient has a Body Mass Index (BMI) > 40 kg/m^2;
 
3. Patient is not able to walk independently (inability to walk at least 10 consecutive meters without a walking aid);
 
4. Patient has had a surgical intervention during the past 30 days for treatment of painful joint or its underlying etiology;
 
5. Patient has had previous open surgeries on the affected joint other than arthroscopy;
 
6. Patient has active infectious collagen diseases (i.e. scleroderma) or any other condition that would interfere with wound healing;
 
7. Patient is allergic to poly (p-dioxanon), IRGACARE®* MP (triclosan) or D&C Violet No. 2;
 
8. Patient has diabetes with poor control, defined as fasting plasma glucose (FPG) ≥ 10.0 mmol/L;
 
9. Patient has a history of immunosuppressive drug use, including steroids, within the last 6 months;
 
10. Patient has undergone chemotherapy or radiation within the last 6 months prior to study enrollment or is scheduled to do so during the study period;
 
11. Patient has known personal or family history of keloid formation or hypertrophy;
 
12. Patient has other dermatologic conditions known to impair wound healing;
 
13. Patient is participating in any other investigational drug (within 30 days or 5 half-lives of an investigational drug) or device study;
 
14. Patient has any physical or psychological condition which would impair study participation; and
 
15. Patient is judged unsuitable for study participation by the investigator for any other reason.
 

Study Product:	Knotless Tissue Control Device

Statistical Methods:	
All efficacy endpoints will be summarized descriptively by treatment group. The continuous variables will be summarized descriptively by number of subjects, mean, standard deviation, minimum, and maximum. Categorical data will be summarized descriptively by frequencies along with the associated percentages.
 
In addition, for the primary efficacy endpoint, a one-sided 97.5% confidence interval for the difference in treatment group means (Mean [REDACTED] closure time minus the Mean closure time for conventional suture) will be constructed using the t-distribution.
 
The primary efficacy endpoint will be analyzed using the mITT and Per-Protocol analysis sets. The ITT analysis will be considered as the primary analysis. All secondary efficacy endpoints will be analyzed using the mITT analysis set.
 
All secondary safety endpoints will be summarized descriptively by treatment group for the Safety analysis set using available data. The continuous variables will be summarized descriptively by number of subjects, mean, standard deviation, minimum, and maximum. Categorical data will be summarized descriptively by frequencies along with the associated percentages. No inferential statistics will be generated for the secondary safety endpoints.

-----------------------------	---

## SCHEDULE OF EVENTS

Event	Visit 1	Visit 2	Visit 3	Visit 4	Visit 5
	Baseline/ Screening a	Randomization	Procedure	Post-Op through Discharge b	30-42 days c (post procedure)
Informed consent	X				
IWRS/IVRS d		X			
Inclusion/Exclusion Criteria	X	X			
Urine/blood pregnancy test	X				
Demographics	X				
Medical/Surgical history	X		X		
Physical examination e	X			X	X
Knee pain VAS	X			X	X
EQ-5D-3L	X			X	X
Concomitant medications f	X	X	X	X	X
Length of stay g				X	
Health Economic Data Collection				X	
Procedural data h			X		
Adverse events			X	X	X
Wound complication assessment			X	X	X
SSI/ASEPSIS score i				X	X
AIRE score				X	X
Study completion					X

- a. To be performed within 30 days of surgery.
- b. Physical examination, knee pain VAS, EQ-5D-3L and AIRE score will be collect on 3-5 days after surgery.
- c. Unless withdrawn from the study, subject's status will be confirmed at the time of in-person visit at 30-42 days following surgery. If possible, an in-person visit will be scheduled to confirm status for patients withdrawn prematurely from the study for any reason.
- d. Interactive web response system/ Interactive voice response system.
- e. The physical examination at baseline/screening visit includes height, weight and ROM of knee, and the post-procedure physical examination only includes ROM of knee.
- f. Including pain medications and antibiotics (except for anesthesia medications).
- g. Defined as time between procedure and discharge.
- h. Procedure time, overall OR time, intra-operative device failure rates, operating room resource utilization (if applicable), and anesthesia method (e.g., general or lumbar anesthesia).
- i. ASEPSIS score will be applied only after SSI confirmed.

## PROTOCOL-SPECIFIC ACRONYMS AND ABBREVIATIONS

Acronyms/Abbreviations	Terms
ADE	Adverse Device Effect
AE	Adverse Event
AIRE	Acute Inflammatory Response Evaluation
ASADE	Anticipated Serious Adverse Device Effect
BMI	Body Mass Index
CDC	Centers for Disease Control
CFDA	China Food and Drug Administration
CFR	Code of Federal Regulations
CHU	Complaint Handling Unit
EC	Ethics Committee
eCRF	Electronic Case Report Form
ESC	████████ Surgical Care
EDC	Electronic Data Capture
FPG	Fasting Plasma Glucose
GCP	Good Clinical Practice
ICD	Informed Consent Document
MITT	modified Intent-to-Treat
IVRS	Interactive Voice Response System
IWRS	Interactive Web Response System
MedDRA	Medical Dictionary for Regulatory Activities
OR	Operating Room
PI	Principal Investigator
PP	Per-Protocol
QoL	Quality of Life
ROM	Range of Motion
SADE	Serious Adverse Device Effect
SAE	Serious Adverse Event
SAP	Statistical Analysis Plan
SOC	Standard of Care
SSI	Surgical Site Infection
TKA	Total Knee Arthroplasty
TSA	Topical Skin Adhesive
USP	United States Pharmacopeia
VAS	Visual Analogue Scale

## 1.0 Introduction

### 1.1 Knee Joint Disorder and TKA

The knee joint is a complicated structure bound by a host of tendonous and ligamentous structures prone to acute and chronic injury. Since the hyaline cartilage covered weight bearing surfaces are separated by menisci, body weight, impact and trauma gradually draw them together over time. Once the joint space is compromised by meniscal thinning, hyaline surfaces come into contact with one another, degenerative processes begin and osteoarthritis develops. Other types of disease that may affect the knee include rheumatoid arthritis, post-traumatic arthritis, osteonecrosis and cancer. Irrespective of the underlying degenerative process, pain and decreased range of motion begin to impact the patients' quality of life. Gradually, fewer daily activities are performed and systemic and mental healths are affected.

First performed in the 1960's, total knee arthroplasty (TKA) is a historically successful procedure that removes diseased portions of the knee joint and replaces them with prosthetic implants. Although there are many causes of knee joint deterioration, the primary indication for a patient to undergo TKA is to address the pain and loss of joint function secondary to advanced osteoarthritis.

Over the past 20 years, due to ageing, development of diagnostic and surgical technologies, as well as the continuous improvement of surgical instruments, the number of TKA surgery continues to grow over time [1, 2]. And the number could still continue growing rapidly in the next two decades [3-5], and further increasing the burden of health-care institutions. Currently, interrupted suture was still in use to close surgical incision during the operation. In comparison to the traditional continuous suture technique, interrupted suture may in some degree improve the suture strength for the surgical incision, in order to meet the need of early function exercise. However, interrupted technique has a relatively low suture efficacy, thus may prolong the suturing and operation time, when compared to the continuous technique. Reducing the operation time is associated with reduced risk of incisional complications, especially surgical site infection [6], which as a result, can be catastrophic for the TKA surgery outcome.

████████ have a unique barbed design, which, theoretically, allows physicians to perform highly efficient continuous suture, and to improve operation efficiency. By reducing the operation time, the new product can achieve the same safety and effectiveness as compared with the interrupted suture technique [5, 7-10].

This study was designed to verify that ██████████ can improve the operation efficacy, can reduce the suturing and operation time as well as meet the clinical demand for suture safety, as compared to traditional interrupted suture technique during TKA surgery.

[figure not shown]
### 1.2 Study Device Description

████████ is an antibacterial (polydioxanone) monofilament, synthetic absorbable device prepared from polydioxanone (p-dioxanone). The device contains IRGACARE®1 MP (triclosan), a broad spectrum antibacterial agent. ██████████

████████ monofilament is dyed with D&C Violet No. 2. ██████████ consists of an absorbable thread with unidirectional anchors, equipped with a surgical needle at one end and a fixation tab at the other (Figure 1). The anchors and fixation tab design allows for tissue approximation without the need to tie surgical knots. The cross-sectional area of the ██████████ core is comparable to the cross-sectional area of a United States

Pharmacopeia (USP) suture with the same designation, i.e., 0, 1, 2-0, 3-0. [REDACTED] straight tensile strength is stronger than the knot tensile strength for a USP polydioxanone suture of the equivalent size. Polydioxanone has been found to be non-allergenic, non-pyrogenic, and to elicit only a slight tissue reaction during absorption.

Figure 1: [REDACTED] (with Anchor and Fixation Tab Enlargements)

## 2.0 Study Objectives

The primary objective of this prospective, randomized controlled study is to evaluate the wound closure efficiency of [REDACTED] compared to conventional sutures in patients undergoing TKA. For the purpose of this study, wound closure efficiency is defined as the total time required to close the surgical incisions in patients undergoing TKA procedures using [REDACTED] compared to those using traditional sutures. Secondary objectives will include the evaluation of differences in overall surgical procedure time, operation room (OR) time, length of stay, procedure costs, quality of life measures including pain, and range of motion (ROM). In addition, the difference in the safety profiles for both wound closure procedures will be evaluated through the analysis of the incidence of wound complications including dehiscence, wound infections, and other adverse events.

### 2.1 Primary Endpoints:

The primary endpoint will be the total time required to close the surgical incisions between treatment groups. The time to close each surgical incision is defined as the time in minutes between placements of the first suture throws in the deep tissue to the completion of Intradermal layer closure (capturing the suturing time only).

### 2.2 Secondary Efficacy Endpoints:

1. Duration of procedure: defined as the time in minutes elapsed from first incision to the skin closure.

2. Overall operating room (OR) time: defined as the time in minutes from anesthesia to exiting the OR;
3. Length of stay between surgery and discharge.
4. TKA related QoL assessments:
  - a. Knee Pain: pain at rest and pain during mobilization is measured using a 10 centimeter Visual Analogue Scale (VAS) in which patient is asked to describe degree of pain with 0 being no pain and 10 being the worst pain.
  - b. Health-related Quality of Life (EQ-5D-3L): patient is asked to confirm his/her health state by selecting the most appropriate level for each of the following 5 dimensions. Refer to Table 1.
    - Mobility
    - Self-care
    - Usual activities
    - Pain/discomfort
    - Anxiety/depression

**Table 1: EQ-5D-3L**

**By placing a tick in one box in each group below, please indicate which statements best describe your own health state today.**

**Mobility**

I have no problems in walking about	
I have moderate problems in walking about	
I am unable to walk about	

**Self-care**

I have no problems washing or dressing myself	
I have moderate problems washing or dressing myself	
I am unable to wash or dress myself	

**Usual Activities (i.e work, study, housework, family or leisure activities)**

I have no problems doing my usual activities	
I have moderate problems doing my usual activities	
I am unable to do my usual activities	

**Pain/Discomfort:**

I have no pain or discomfort	
I have moderate pain or discomfort	
I have extreme pain or discomfort	

[figure not shown]
**Anxiety/Depression**

I am not anxious or depressed	
I am moderate anxious or depressed	
I am extremely anxious or depressed	

To help people say how good or bad a health state is, we have drawn a scale (rather like a thermometer) on which the best state you can imagine is marked **100** and the worst state you can imagine is marked **0**.

We would like you to indicate on this scale how good or bad your own health is today, in your opinion. Please do this by drawing a line from the box below to whichever point on the scale indicates how good or bad your health state is today.

Your own  
health state  
today

### **2.3 Secondary Safety Endpoints:**

The following data will be summarized by treatment group. The continuous variables will be summarized descriptively by number of subjects, mean, standard deviation, minimum, and maximum. Categorical data will be summarized descriptively by frequencies along with the associated percentages.

1. The incidence of SSI following surgery as defined by:

a. CDC criteria:

1) Superficial incisional SSI:

Infection occurs within 30 days after the operation and infection involves only skin or subcutaneous tissue of the incision and at least one of the following:

- Purulent drainage, with or without laboratory confirmation, from the superficial incision;
- Organisms isolated from an aseptically obtained culture of fluid or tissue from the superficial incision;
- At least one of the following signs or symptoms of infection: pain or tenderness, localized swelling, redness, or heat and superficial incision, is deliberately opened by surgeon, unless incision is culture-negative;
- Diagnosis of superficial incisional SSI by the surgeon or attending physician.

Do not report the following conditions as SSI:

- Stitch abscess (minimal inflammation and discharge confined to the points of suture penetration);
- Infection of an episiotomy or new born circumcision site;
- Infected burn wound;
- Incisional SSI that extends into the fascial and muscle layers (see deep incisional SSI).

Note: Specific criteria are used for identifying infected episiotomy and circumcision sites and burn wounds.

2) Deep incisional SSI:

Infection occurs within 30 days after the operation if no implant is left in place or within 1 year if implant is in place and the infection appears to, be related to the operation and infection involves deep soft tissues (e.g., fascial and muscle layers) of the incision and at least one of the following:

- Purulent drainage from the deep incision but not from the organ/space component of the surgical site;
- A deep incision spontaneously dehisces or is deliberately opened by a surgeon when the patient has at least one of the following signs or symptoms: fever ( $>38^{\circ}\text{C}$ ), localized pain, or tenderness, unless site is culture-negative;
- An abscess or other evidence of infection involving the deep incision is found on direct examination, during reoperation, or by histopathologic or radiologic examination;
- Diagnosis of a deep incisional SSI by a surgeon or attending physician.

Notes:

- Report infection that involves both superficial and deep incision sites as deep incisional SSI;
- Report an organ/space SSI that drains through the incision as a deep incisional SSI.

3) Organ/Space SSI:

Infection occurs within 30 days after the operation if no implant is left in place or within 1 year if implant is in place and the infection appears to, be related to the operation and infection

involves any part of the anatomy (e.g., organs or spaces), other than the incision, which was opened or manipulated during an operation and at least one of the following:

- Purulent drainage from a drain that is placed through a stab wound into the organ/space;
- Organisms isolated from an aseptically obtained culture of fluid or tissue in the organ/space;
- An abscess or other evidence of infection involving the organ/space that is found on direct examination, during reoperation, or by histopathologic or radiologic examination;
- Diagnosis of an organ/space SSI by a surgeon or attending physician.

No confirmatory culture will be required unless deemed by the physician per local standard of care to provide appropriate treatment to subject.

b. ASEPSIS Score (only for patients with confirmed SSI): assesses severity of wound infection using numerical scoring (as opposed to the CDC's absence or presence of SSI and type). The ASEPSIS Wound Score evaluates wound characteristics and additional treatments as predictors of infection that may develop once the subject leaves the hospital. These include the presence of serous exudates, erythema, purulent exudates, separation of deep tissues, antibiotics, drainage of pus, wound debridement, isolation of bacteria, and requirement for inpatient stay. Surgeons assess each parameter and provide a numerical score based upon objective criteria of wound appearance and clinical consequences of the infection. Extra points were added for antibiotic treatment of SSI (10 points), drainage of pus under local anesthesia (5 points), debridement of the wound under general anesthesia (10 points), isolation of bacteria from the wound (10 points), and an inpatient stay of more than 14 days (5 points). An overall score, ranging from 0 to 100, is then calculated to define wound severity according to the proportion of the wound affected by each of these characteristics. Refer to Table 2:

2. Use Acute Inflammatory Response Evaluation (AIRE) score measuring inflammatory tissue reaction. Of note, an AE will be reported when the score is >1. Refer to Table 3;
3. Incidence of wound separation or dehiscence requiring intervention;
4. Incidence of delayed wound healing events;
5. Incidence of wound closure related adverse events and serious adverse events;

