**Table 3: Acute Inflammatory Response Evaluation (AIRE) Score**

Score	Erythema	Oedema	Pain	Temperature
0	None observed	None observed	None	None
1	Slight blanching redness along incision closure line	Slight increase in tissue firmness (turgor)	Pain at site with pressure	Slightly warmer compared to adjacent skin
2	Moderate redness extending < 2 mm	Pitting of skin around incision with mild pressure	Pain at site with touch	Definitely warmer compared to adjacent skin
3	Intense redness extending > 2 mm	Tense firmness of skin around incision	Continuous pain	Radiating heat at incision site

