
### **3.3.2 Blinding**

Blinding practices for this study will include the following:

**Patients:** Patients will be informed of the 1:1 randomization between the different suturing material and technique, but will remain blinded as to which implant they actually received until after they have completed all study follow-up.

**Implanting surgeon:** It is not possible to blind the implanting physician due to the different suturing technique and products.

**Medical Records:** All medical records (source documents) documenting the implant procedure through hospital discharge and all follow-ups will not be blinded because the devices used will be described in the operation record.

**Monitors:** Monitors will not be blinded because the detachable labels provided with the product identify the product and may be used in the study device accountability records and patient research file for the purpose of device accountability and source document validation.

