## **6.0 Adverse Event**

### **6.1 Definitions**

#### **6.1.1 Anticipated Adverse Events**

There are immediate post-operative events that are changes from the baseline condition of the Subject, but are expected events resulting from the surgery. If these events occur, they should be recorded in the Subject's medical record and reported forward as AEs to the study sponsor.

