#### **6.1.4 Expected Morbidity/Anticipated Adverse Events**

An expected morbidity/procedural complication is defined as an AE that is known to be common or usual in nature, severity, or incidence during TKA in patients with knee osteoarthritis or other diseases.

Postoperative pain and fever is expected and will not be documented as an adverse event unless the Investigator considers the pain or fever to exceed that normally anticipated following a TKA procedure.

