Infection occurs within 30 days after the operation if no implant is left in place or within 1 year if implant is in place and the infection appears to, be related to the operation and infection involves any part of the anatomy (e.g., organs or spaces), other than the incision, which was opened or manipulated during an operation and at least one of the following:

- Purulent drainage from a drain that is placed through a stab wound into the organ/space;
- Organisms isolated from an aseptically obtained culture of fluid or tissue in the organ/space;
- An abscess or other evidence of infection involving the organ/space that is found on direct examination, during reoperation, or by histopathologic or radiologic examination;
- Diagnosis of an organ/space SSI by a surgeon or attending physician.

No confirmatory culture will be required unless deemed by the physician per local standard of care to provide appropriate treatment to subject.

b. ASEPSIS Score (only for patients with confirmed SSI): assesses severity of wound infection using numerical scoring (as opposed to the CDC's absence or

presence of SSI and type). The ASEPSIS Wound Score evaluates would characteristics and additional treatments as predictors of infection that may develop once the subject leaves the hospital. These include the presence of serous exudates, erythema, purulent exudates, separation of deep tissues, antibiotics, drainage of pus, wound debridement, isolation of bacteria, and requirement for inpatient stay. Surgeons assess each parameter and provide a numerical score based upon objective criteria of wound appearance and clinical consequences of the infection. Extra points were added for antibiotic treatment of SSI (10 points), drainage of pus under local anesthesia (5 points), debridement of the wound under general anesthesia (10 points), isolation of bacteria from the wound (10 points), and an inpatient stay of more than 14 days (5 points). An overall score, ranging from 0 to 100, is then calculated to define wound severity according to the proportion of the wound affected by each of these characteristics ^[2, 3]. Refer to Table 2;

2. Use Acute Inflammatory Response Evaluation (AIRE) score measuring inflammatory tissue reaction. Of note, an AE will be reported when the score is >1 . Refer to Table 3;
3. Incidence of wound separation or dehiscence requiring intervention;
4. Incidence of delayed wound healing events;

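### AIRE wound pain of 2 or 3 at the day 3-5 visit falls under two conflicting AE rules, and nothing says which prevails

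*Protocol*

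**What the plan says.** Protocol 2.3 item 2 introduces the AIRE score and adds: "Of note, an AE will be reported when the score is >1". SAP 1.2.3 item 2 carries the same rule: "an AE will be reported when the score is >1". Table 3 of the protocol grades erythema, oedema, pain and temperature from 0 to 3. Pain scores 2 for "Pain at site with touch" and 3 when it is continuous. Note b to the protocol's Schedule of Events fixes the timing of the post-operative assessment: "Physical examination, knee pain VAS, EQ-5D-3L and AIRE score will be collect on 3-5 days after surgery". AIRE is scored again at Visit 5, 30 to 42 days after surgery.

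Protocol 6.1.4 sets a different rule for pain: "Postoperative pain and fever is expected and will not be documented as an adverse event unless the Investigator considers the pain or fever to exceed" what is normally to be expected after the operation. It has no time limit and does not mention AIRE. The SAP repeats the AIRE trigger but not this exemption.

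The endpoint affected is item 6 of the secondary safety endpoints in the synopsis: "Incidence of adverse events (AEs) and serious adverse events (SAEs) associated with wound closure". Protocol 4.5.5 and SAP 3.3 make all safety analysis descriptive.

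**The concern.** Pain on touching a knee incision three to five days after arthroplasty is a finding that an investigator may well call normal. The AIRE trigger makes it an AE, and 6.1.4 says it is not one. Neither rule refers to the other, and no text ranks them.

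The number of wound-closure AEs for the same set of wounds therefore depends on which sentence a site follows. With no test planned on safety, the displayed counts are the whole result, so their definition should not be open. Under 6.1.4 the count also rests on the investigator's judgement, in a trial where the protocol says of the surgeon: "It is not possible to blind the implanting physician due to the different suturing technique and products". If the exemption is followed, no planned table shows how many patients had incision pain of grade 2 or 3. The AIRE result is summarised only as a 0 to 12 total.

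**Working it through.** **Step 1. Does pain of 2 or 3 always meet the trigger?** The rule does not say whether >1 refers to a single sign or to the total. Four signs graded 0 to 3 give 4^4 = 256 combinations, of which 2 × 4^3 = 128 have pain of 2 or 3. In all 128 the highest sign is at least 2 and the total is at least 2. The trigger fires on either reading, so the conflict does not depend on that question. (Another 11 combinations have no sign above 1 but a total above 1. They are a separate ambiguity.)

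**Step 2. The two rules side by side.** Take pain of 2 on day 4, judged normal by the investigator.
- Protocol 2.3 item 2 and SAP 1.2.3 item 2: report an AE.
- Protocol 6.1.4: do not document an AE.

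The conflict concerns the pain sign only. Section 6.1.4 does not exempt erythema, oedema or local temperature.

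**Step 3. Denominator.** The plan's own figure reproduces: 77 / (1 − 0.16) = 91.7, rounded up to 92 per arm.

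**Step 4. Size of the difference.** The documents supply none of the rates needed, so all are assumed:
- p, share with AIRE pain of 2 or more at days 3-5: 20% to 80%
- r, share of those judged excessive: 5% to 30%
- q, share with another closure AE: 10%, independent of pain
- every pain AE is attributed to wound closure

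Incidence under the trigger = 1 − (1 − p)(1 − q). Incidence under the exemption = 1 − (1 − p·r)(1 − q).

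At p = 60% and r = 10%:
- trigger: 1 − 0.40 × 0.90 = 64%, about 59 of 92
- exemption: 1 − 0.94 × 0.90 = 15.4%, about 14 of 92

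| p | Trigger | Exemption, r = 5% | r = 10% | r = 30% |
|---|---|---|---|---|
| 20% | 28% | 10.9% | 11.8% | 15.4% |
| 40% | 46% | 11.8% | 13.6% | 20.8% |
| 60% | 64% | 12.7% | 15.4% | 26.2% |
| 80% | 82% | 13.6% | 17.2% | 31.6% |

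**Step 5. Does this bias the arms?** With the same p, q and r in both arms, the expected arm difference is zero under either rule and under any mix of rules across sites. A systematic difference needs r to differ by arm. The table gives the exact binomial probability, with 92 per arm and p = 60%, that control exceeds barbed by 10 points or more.

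| Case | Probability |
|---|---|
| Pain AEs, trigger | 7.6% |
| Pain AEs, exemption, r = 10% in both arms | 0.2% |
| Pain AEs, exemption, r = 20% control, 10% barbed (12% vs 6%) | 15% |
| Pain AEs, exemption, r = 30% control, 10% barbed (18% vs 6%) | 64% |
| Same as the last row, with other closure AEs included (26.2% vs 15.4%) | 53% |

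The large values come from the assumed threefold difference in judgement between arms, not from the conflict of rules.

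**The case against.** The best defence is that the AIRE rule is a graded, incision-specific trigger for tissue inflammation, while 6.1.4 deals with the general pain of a knee replacement. A site could reasonably let the specific rule govern. That is a sensible reading, but no text adopts it. Section 6.1.4 covers postoperative pain without restriction and is itself specific to pain and fever, so the ambiguity stands.

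Several limits on the consequences also stand. Knee pain on the visual analogue scale is collected at the same visits and summarised by arm, and EQ-5D-3L pain and pain medication are recorded. None of these is specific to the incision, but a reader should not infer that a real pain difference could show only through the AIRE total. Relatedness is judged separately under protocol 6.1.9, so not every pain AE need enter the closure count. SAP 3.3.2 tabulates AEs by preferred term, which lets pain be separated from other wound events.

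A reader might also count 6.1.1 as a second contradiction, because it wants expected post-operative events "reported forward as AEs to the study sponsor". It names neither AIRE nor pain, and 6.1.4 reads naturally as an exception to it. It is background only.

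Finally, a reader might infer that about 8 sites following different rules, with no centre adjustment, would distort the comparison. Patients are randomised 1:1, so a site's rule applies to both of its arms, and Step 5 shows no expected difference from that alone.

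**Conclusion.** The conflict is real and lies in the current text: protocol 2.3 item 2 and SAP 1.2.3 item 2 against protocol 6.1.4, for AIRE pain of 2 or 3 at the day 3-5 visit. It makes the level of a named safety endpoint depend on the rule followed, illustratively 64% against 15% on the assumptions in Step 4. No rate there comes from the documents, and the gap shrinks if fewer patients have such pain or fewer of the events are attributed to closure.

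The documents do not support the stronger claim that the conflict biases the arm comparison. That would require unblinded judgement under 6.1.4 to differ by arm, which is possible but assumed. The primary endpoint is unaffected, and no test or decision rule changes. Severity is minor, at the low end.

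**What to change.** 1. In protocol 2.3 item 2 and SAP 1.2.3 item 2, state that incision-site pain at Visit 4 is exempt from the AIRE trigger unless the investigator considers it more than normally anticipated, citing protocol 6.1.4 by document because the SAP has no such section. State that the trigger applies to all four signs at Visit 5.
2. In protocol 6.1.4, limit the exemption for AIRE-scored incision pain to the period through Visit 4 and refer to 2.3 item 2. Without this limit the two rules would still clash at Visit 5. In 6.1.1, add that pain and fever are excepted as set out in 6.1.4.
3. In SAP 3.3, add the number and percentage with AIRE pain of 2 or more, by arm, at Visit 4 and at Visit 5, in the Safety set, taken from the recorded scores.

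The cost is a few sentences and one table row per visit. The individual scores are already needed to form the AIRE total. Expected Visit 4 incision pain leaves the AE tables, and the pain AE count still rests on investigator judgement. The new row offsets both, because its arm comparison does not depend on what was reported as an AE. It does not address who scores AIRE or whether that person is blinded, which the documents do not say.
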